6.2.7 Management of Diarrhea

Appearance of Grade 1-2 diarrhea attributed to study drug toxicity may be treated with supportive care such as loperamide, initiated at the earliest onset (for example 4 mg orally followed by 2 mg orally every 2 hours until resolution of diarrhea).

6.2.8 Management of Hyperlipidemia and Hyperglycemia

Treatment of hyperlipidemia should take into account the pre-treatment status and dietary habits of the patient. Blood test to monitor hyperlipidemia must be taken in the fasting state. Grade 2 hypercholesterolemia (>300 mg/dL or 7.75 mmol/L) or Grade 2 hypertriglyceridemia ($>2.5 \times$ ULN) should be treated with a 3-hydroxy-3-methyl-glutaryl (HMG)-CoA reductase inhibitor (e.g., atorvastatin, pravastatin) or appropriate lipid-lowering medication, in addition to diet.

Note: Concomitant therapy with fibrates and an HMG-CoA reductase inhibitor is associated with an increased risk of a rare but serious skeletal muscle toxicity manifested by rhabdomyolysis, markedly elevated creatine kinase (CPK) levels and myoglobinuria, acute renal failure and sometimes death. The risk versus benefit of using this therapy should be determined for individual patients based on their risk of cardiovascular complications of hyperlipidemia.

Dyslipidemia (including hypercholesterolemia and hypertriglyceridemia) has been reported in patients taking everolimus. Monitoring of blood cholesterol and triglycerides prior to the start of everolimus therapy and periodically thereafter as well as management with appropriate medical therapy is recommended.

Hyperglycemia has been reported in patients taking everolimus. Monitoring of fasting serum glucose is recommended prior to the start of everolimus and periodically thereafter. More frequent monitoring is recommended when everolimus is co-administered with other drugs that may induce hyperglycemia. Optimal glycemic control should be achieved before starting a patient on everolimus.

6.2.9 Management of Non-Infectious Pneumonitis

Non-infectious pneumonitis is a class effect of rapamycin derivatives. Cases of non-infectious pneumonitis (including interstitial lung disease) have also been described in patients taking

CONFIDENTIAL

STUDY DRUG(S): EVEROLIMUS
FINAL PROTOCOL DATE: 19 JUNE 2014

SCRI INNOVATIONS STUDY NUMBER: BRE 212
VERSION 1.0

everolimus. Some of these have been severe and on rare occasions, a fatal outcome was observed.

- A diagnosis of non-infectious pneumonitis should be considered in patients presenting with non-specific respiratory signs and symptoms such as hypoxia, pleural effusion, cough or dyspnea, and in whom infectious, neoplastic and other non-medicinal causes have been excluded by means of appropriate investigations. Opportunistic infections such as PJP should be ruled out in the differential diagnosis of non-infectious pneumonitis. Patients should be advised to report promptly any new or worsening respiratory symptoms.

Patients who develop radiological changes suggestive of non-infectious pneumonitis and have few or no symptoms may continue everolimus therapy without dose alteration.

If symptoms are moderate (grade 2), consideration should be given to interruption of therapy until symptoms improve. The use of corticosteroids may be indicated. Everolimus may be reintroduced at a daily dose approximately 50% lower than the dose previously administered.

For cases of grade 3 non-infectious pneumonitis, interrupt everolimus until resolution to less than or equal to grade 1. Everolimus may be re-initiated at a daily dose approximately 50% lower than the dose previously administered depending on the individual clinical circumstances. If toxicity recurs at grade 3, consider discontinuation of everolimus. For cases of grade 4 non-infectious pneumonitis, everolimus therapy should be discontinued. Corticosteroids may be indicated until clinical symptoms resolve.

For patients who require use of corticosteroids for treatment of non-infectious pneumonitis, prophylaxis for pneumocystis jirovecii pneumonia (PJP) may be considered. The two compounds studied most extensively for prophylaxis against PJP have been trimethoprim-sulfamethoxazole, given orally, and pentamidine, given as an aerosol.

Patients in this study will be routinely questioned as to the presence of new or changed pulmonary symptoms consistent with pneumonitis. Moreover, potential lung radiological changes can be detected by the chest CT/MRI scans that are performed on all patients every 2 cycles for tumor assessment according to the schedule of events (Appendix D). Pulmonary function tests (PFTs) will be conducted, if clinically indicated, to monitor for pneumonitis. If non-infectious pneumonitis develops, the guidelines in Table 5 should be followed. Consultation with a pulmonologist is recommended for any case of pneumonitis that develops during the study.

CONFIDENTIAL

STUDY DRUG(S): EVEROLIMUS
FINAL PROTOCOL DATE: 19 JUNE 2014

SCRI INNOVATIONS STUDY NUMBER: BRE 212
VERSION 1.0

Table 5 Management of Non-Infectious Pneumonitis Due to Everolimus

Worst Grade Pneumonitis	Required Investigations	Management of Pneumonitis	Everolimus Dose Adjustment
Grade 1 (Asymptomatic, radiographic findings only)	CT scans with lung windows. Consider room air O ₂ saturation at rest	No specific therapy is required	Administer 100% of everolimus dose. Initiate appropriate monitoring.
Grade 2 (Symptomatic, not interfering with Activities of Daily Living)	CT scan with lung windows. Consider pulmonary function testing including: spirometry, DLCO, and room air O ₂ saturation at rest. Consider a bronchoscopy with biopsy and/or BAL. Monitor at each visit until return to ≤ Grade 1. Return to initial monitoring frequency if no recurrence.	Symptomatic only. Consider corticosteroids and/or other supportive therapy if symptoms are troublesome.	Rule out infection and consider interruption of everolimus until symptoms improve to ≤ Grade 1. Re-introduce everolimus at one dose level lower. Discontinue everolimus if failure to recover within ≤ 28 days.
Grade 3 (Symptomatic, Interfering with Activities of Daily Living. O ₂ indicated)	CT scan with lung windows and pulmonary function testing including: spirometry, DLCO, and room air O ₂ saturation at rest. Consider a bronchoscopy with biopsy and/or BAL. Monitor at each visit until return to ≤ Grade 1. Return to initial monitoring frequency if no recurrence.	Consider corticosteroids if infective origin is ruled out. Taper as medically indicated.	Rule out infection and interrupt everolimus until symptoms improve to ≤ Grade 1. Consider reintroducing everolimus at one dose level lower. Discontinue everolimus if failure to recover within ≤ 28 days. If toxicity recurs at Grade 3, consider discontinuation.
Grade 4 (Life-threatening, ventilatory support indicated)	CT scan with lung windows and required pulmonary function testing, if possible, including: spirometry, DLCO, and room air O ₂ saturation at rest. Bronchoscopy with biopsy and/or BAL is recommended if possible. Monitor at each visit until return to ≤ Grade 1. Return to initial monitoring frequency if no recurrence.	Consider corticosteroids if infective origin is ruled out. Taper as medically indicated.	Rule out infection and discontinue everolimus.

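### Section 6.2.9 lets pneumonitis patients with few symptoms stay on unchanged everolimus although Table 5 grades them as Grade 2, and Table 4's Grade 4 row lacks the pneumonitis exception

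*Protocol*

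**What the plan says.** Three places in the protocol govern the everolimus dose when pneumonitis occurs.

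- **Section 6.2.9, running text.** On mild cases: "Patients who develop radiological changes suggestive of non-infectious pneumonitis and have few or no symptoms may continue everolimus therapy without dose alteration". On the next step up: "If symptoms are moderate (grade 2), consideration should be given to interruption of therapy until symptoms improve". On the most severe: "For cases of grade 4 non-infectious pneumonitis, everolimus therapy should be discontinued". The section then says that the guidelines in Table 5 should be followed if non-infectious pneumonitis develops.
- **Table 5 (within Section 6.2.9).** The first row is "Grade 1 (Asymptomatic, radiographic findings only", with the dose instruction "Administer 100% of everolimus dose. Initiate appropriate monitoring". The second row is "Grade 2 (Symptomatic, not interfering with Activities of Daily Living". Its instructions include "Monitor at each visit until return to" Grade 1 or better, and "Rule out infection and consider interruption of everolimus until symptoms improve to" Grade 1 or better. They go on to re-introduction one dose level lower, and to discontinuation if the patient has not recovered within 28 days. The Grade 4 row says to discontinue.
- **Table 4 (Section 6.2).** The first row, which covers Grade 3 events, excepts pneumonitis and points to Table 5. The row for Grade 4 events carries no exception. It says to hold everolimus until recovery and then restart one level lower.

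**The concern.** The running text and the table draw the line between Grade 1 and Grade 2 in different places. The text groups patients who have a few symptoms with those who have none and allows both an unchanged dose. The table lets only the second group count as Grade 1. A patient with radiographic changes and a slight cough falls on opposite sides of the line depending on which part of the section the site reads.

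Table 4 raises a second difficulty. Because the exception is printed in one row and absent from another, a reader could infer that Grade 4 pneumonitis is handled by Table 4, which allows a restart, rather than by Table 5, which does not. The routing adds to this: the introductions to Sections 6 and 6.2 send readers to Tables 3 and 4 for non-hematologic toxicity without naming Table 5.

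What is at stake is patient safety. The protocol itself says that some cases of this toxicity have been severe and, rarely, fatal. About nine sites apply the instructions (Section 5), and there is no data monitoring committee (Section 10.6).

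**Working it through.** The plan states no figure on this point, so the check sets the instructions side by side.

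**Step 1: the Grade 1/Grade 2 boundary.**

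| Patient with radiographic changes | Section 6.2.9 text | Table 5 |
|---|---|---|
| No symptoms | Continue, dose unchanged | Grade 1: full dose, start monitoring |
| Few or mild symptoms, daily living unaffected | Continue, dose unchanged | Grade 2 |
| Moderate symptoms, daily living unaffected | Grade 2: consider interruption, restart about 50% lower | Grade 2 |

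The middle row is the mismatch. Table 5's Grade 2 sets no minimum severity, so any symptom is enough.

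**Step 2: what the middle-row patient could miss.**

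- Considering interruption: attached to Grade 2 in both places, but not to the 6.2.9 permission.
- Monitoring at each visit until Grade 1 or better: Table 5 Grade 2 only.
- Re-introduction one level lower: this follows an interruption, so it is missed if interruption is never considered.
- Discontinuation if not recovered within 28 days: this appears in Table 5 and nowhere in the 6.2.9 text. Table 4 has a general 28-day rule, but it applies to toxicity that required an interruption, so a patient continued unchanged would not trigger it. Table 5 does not say when its 28 days begin.

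**Step 3: is the size of the dose reduction also inconsistent?** No. Table 1 gives 10 mg daily, 5 mg daily and 5 mg every other day, the last being 5 / 2 = 2.5 mg per day. The steps are 1 − 5/10 = 50% and 1 − 2.5/5 = 50%. The text's reduction of about 50% and the table's one dose level are the same thing.

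**Step 4: Grade 4.**

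| Place | Instruction for Grade 4 |
|---|---|
| Section 6.2.9 text | Discontinue |
| Table 5, Grade 4 row | Discontinue |
| Table 4, Grade 4 row | Hold, restart one level lower; no pneumonitis exception |

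Two pneumonitis-specific instructions agree. The general row, read alone, says the opposite.

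**The case against.** The strongest reply is that the protocol already settles which rule applies. Section 6.2.9 directs sites to Table 5, and specific guidance normally overrides a generic Grade 4 row. To rechallenge after Grade 4 pneumonitis, a site would have to ignore the 6.2.9 text, Table 5, the pointer to Table 5 and the exception in Table 4's own first row. This stands, and it is why the point is minor. It does not remove the contrary wording.

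It can also be said that the word moderate in 6.2.9 is only a label for Grade 2, since Section 6 pairs mild to moderate severity with Grades 1 and 2. That is fair. The firm mismatch is then the word few, which cannot be squared with asymptomatic.

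Three stronger readings are tempting, and the documents do not support them.

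- *A site using the 6.2.9 sentence would skip the search for infection.* The same section makes exclusion of infectious causes, including opportunistic infection, part of reaching the diagnosis in a patient with respiratory symptoms. That step is not lost.
- *The text permits a dose that Table 5 forbids.* At Grade 2, Table 5 asks only that interruption be considered. Continuing at full dose is not prohibited.
- *Monitoring would stop altogether.* Table 5's Grade 1 row also calls for monitoring, adverse events are assessed on Day 1 of every cycle, and Section 6.2.9 adds routine questioning about pulmonary symptoms and chest imaging every two cycles. What could be missed is the specific Grade 2 requirement to monitor at each visit until Grade 1 or better.

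**Conclusion.** Both mismatches are confirmed, and the safety rule is wrong as written because it contradicts itself. In Section 6.2.9 the conflict is limited to the grade boundary and the Grade 2 steps that follow from it. In Table 4 it is a missing exception that leaves a contrary instruction in print. Severity is minor, with no effect on endpoints, sample size or analyses.

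Neither mismatch can be sized from the documents. A reader might reach for the 3% pneumonitis rate that Section 1.2 reports from the cited phase III trial and turn it into expected cases among 46 patients. That rate combines Grades 3 and 4. It says nothing about patients at the Grade 1/2 boundary and does not isolate Grade 4, so it measures neither defect.

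The conclusion assumes that a site may act on the 6.2.9 sentence or on Table 4's row without checking Table 5. Where Table 5 is always consulted, the practical effect is nil.

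**What to change.** In Section 6.2.9:

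1. Limit the continue-unchanged sentence to patients with no symptoms, and label them Grade 1.
2. Replace the description of Grade 2 as moderate symptoms with Table 5's definition: symptomatic, with activities of daily living unaffected.
3. Add one sentence stating that the Table 5 Grade 2 steps apply to these patients.

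In Table 4, add to the Grade 4 row the same pneumonitis exception and pointer to Table 5 that the first row carries.

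The cost is a few words and one sentence in Section 6.2.9 and one phrase in Table 4. No procedures, patients or analyses are added, because Table 5 already contains every step.

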6.2.10 Management of Hepatitis Reactivation/Flare

Reactivation of hepatitis B (HBV) has been observed in patients with cancer receiving chemotherapy (Yeo W. et al. 2004). Sporadic cases of hepatitis B reactivation have also been seen in this setting with everolimus. In cancer patients with hepatitis B, whether carriers or in chronic state, use of antivirals during anti-cancer therapy has been shown to reduce the risk of hepatitis B virus reactivation and associated morbidity and mortality (Loomba R. et al. 2008). A detailed assessment of hepatitis B or C medical history and risk factors must be done for all patients at screening, with testing performed prior to the first dose of everolimus.

Patients with known hepatitis, or positive hepatitis serology, are ineligible to enroll in this study.

CONFIDENTIAL

STUDY DRUG(S): EVEROLIMUS
FINAL PROTOCOL DATE: 19 JUNE 2014

SCRI INNOVATIONS STUDY NUMBER: BRE 212
VERSION 1.0

Patients found to have positive hepatitis serology while on study may continue treatment but must receive appropriate hepatitis prophylaxis during the remainder of their treatment with everolimus and for 4 weeks after everolimus is discontinued.

Monitoring and prophylactic treatment for Hepatitis B reactivation

Table 6 provides details of monitoring and prophylactic therapy according to the baseline results of viral load and serologic markers testing.

Table 6 Action Required for Positive Hepatitis B Results While Receiving Everolimus

Test	Result	Result	Result	Result	Result
HBV-DNA	+	+ or -	-	-	-
HBsAg	+ or -	+	-	-	-
HBsAb	+ or -	+ or -	+	+ or -	-
HBcAb	+ or -	+ or -	+ or -	+	-
Recommendation	Prophylaxis treatment should be started 1-2 weeks prior to first dose of everolimus Monitor HBV-DNA every 4 - 8 weeks.		No prophylaxis treatment. Monitor HBV-DNA every 3-4 weeks.		No specific action.

Antiviral prophylaxis therapy should continue for at least 4 weeks after last dose of everolimus. Hepatitis B reactivation definition and management guidelines are defined below in Table 7.

CONFIDENTIAL

STUDY DRUG(S): EVEROLIMUS
FINAL PROTOCOL DATE: 19 JUNE 2014

SCRI INNOVATIONS STUDY NUMBER: BRE 212
VERSION 1.0

Table 7 Guidelines for Management of Hepatitis B

HBV reactivation (with or without clinical signs and symptoms)*	
Baseline Results	Actions
Positive HBV-DNA OR Positive HBsAg Reactivation is defined as: Increase of 1 log in HBV-DNA relative to baseline HBV-DNA value OR New appearance of measurable HBV-DNA	Start a second antiviral medication AND Interrupt everolimus administration until resolution: 
 ≤ baseline HBV-DNA levels If resolution occurs within ≤ 28 days , everolimus should be re-started at one dose lower, if available. (See Table 1 for dose levels available) If the patient is already receiving the lowest dose of everolimus according to the protocol, the patient should restart at the same dose after resolution. Both antiviral therapies should continue at least 4 weeks after last dose of everolimus. If resolution occurs > 28 days , Patients should discontinue everolimus but continue both antiviral therapies at least 4 weeks after last dose of everolimus.
Negative HBV-DNA and HBsAg AND Positive HBsAb (with no prior history of vaccination against HBV), OR Positive HBcAb Reactivation is defined as: New appearance of measurable HBV-DNA	Start first antiviral medication AND Interrupt everolimus administration until resolution: 
 ≤ undetectable (negative) HBV-DNA levels If resolution occurs within ≤ 28 days , everolimus should be re-started at one dose lower, if available (See Table 1 for dose levels available). If the patient is already receiving the lowest dose of everolimus according to the protocol, the patient should restart at the same dose after resolution. Antiviral therapy should continue at least 4 weeks after last dose of everolimus. If resolution occurs > 28 days , discontinue everolimus but continue antiviral therapy at least 4 weeks after last dose of everolimus.

* All reactivations of HBV are to be recorded as Grade 3 (e.g. CTCAE Version 4.0 - Investigations/Other: Viral Reactivation) (<http://evs.nci.nih.gov/ftp1/CTCAE/CTCAE>), unless considered life threatening by the investigator, in which case they should be recorded as Grade 4. Date of viral reactivation is the date on which the rise or reappearance of HBV-DNA was recorded.

Monitoring and Management of Hepatitis C

Two groups of patients will require monitoring every 4 -8 weeks for HCV flare during this study:

- Patients with detectable HCV RNA-PCR test at baseline.
- Patients known to have a history of HCV infection, despite a negative viral load test at baseline (including those that were treated and considered “cured”).

CONFIDENTIAL

STUDY DRUG(S): EVEROLIMUS
FINAL PROTOCOL DATE: 19 JUNE 2014

SCRI INNOVATIONS STUDY NUMBER: BRE 212
VERSION 1.0

Definitions and management guidelines of hepatitis C flare are Table 8.

Table 8 Guidelines for Management of Hepatitis C Flare

Baseline Results	HCV Flare Definition*	HCV Flare Management
Detectable HCV-RNA	> 2 \log_{10} IU/mL increase in HCV-RNA AND ALT elevation > 5 x ULN or 3 x baseline level, whichever is higher.	Discontinue everolimus
Knowledge of past hepatitis C infection with no detectable HCV-RNA	New appearance of detectable HCV-RNA AND ALT elevation > 5 x ULN or 3 x baseline level, whichever is higher.	Discontinue everolimus

* All flares of HCV are to be recorded as Grade 3 (e.g. CTCAE Version 3.0 - Investigations - Other: Viral Flare), unless considered life threatening by the investigator; in which case they should be recorded as Grade 4. Date of viral flare is the date on which both the clinical criteria described above were met (e.g., for a patient whose HCV-RNA increased by 2 logs on 01 JAN 2014 and whose ALT reached > 5 x ULN on 22 JAN 2014, the date of viral flare is 22 JAN 2014).

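### Protocol Section 6.2.10 and its Table 6 do not give one workable prophylaxis instruction for patients found hepatitis-positive on study, and Table 6 contradicts itself on whether it covers baseline or on-treatment results

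*Protocol*

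**What the plan says.** All of this is in the protocol; the SAP does not touch it.

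- **Text rule (Section 6.2.10).** "Patients found to have positive hepatitis serology while on study may continue treatment", but they "must receive appropriate hepatitis prophylaxis during the remainder of their treatment with everolimus and for 4 weeks after everolimus is discontinued". The rule is not limited by marker.
- **Scope of Table 6.** The title reads "Action Required for Positive Hepatitis B Results While Receiving Everolimus". The sentence introducing it reads "Table 6 provides details of monitoring and prophylactic therapy according to the baseline results of viral load and serologic markers testing".
- **Table 6, HBV-DNA or HBsAg positive.** "Prophylaxis treatment should be started 1-2 weeks prior to first dose of everolimus", with HBV-DNA monitoring every 4-8 weeks. A line under the table adds "Antiviral prophylaxis therapy should continue for at least 4 weeks after last dose of everolimus".
- **Table 6, HBV-DNA and HBsAg negative with HBsAb or HBcAb positive.** "No prophylaxis treatment. Monitor HBV-DNA every 3-4 weeks".
- **Table 7, the same antibody-only group, at reactivation.** "Start first antiviral medication AND Interrupt everolimus administration until resolution". The row label counts HBsAb only where there is no history of HBV vaccination. The column is headed as baseline results.
- **Eligibility.** Sections 6.2.10 and 7.1 both bar patients with positive hepatitis serology at screening. Exclusion criterion 9 (Section 3.2) bars known active HBV or HCV infection and, in at-risk patients, a positive HBV-DNA or HCV-RNA PCR.
- **Testing.** Section 7.1 and Appendix D schedule hepatitis testing at baseline only, and only for patients with listed risk factors.

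**The concern.** A site that learns during treatment that a patient carries hepatitis B antibodies will look at the paragraph and at the table below it. The paragraph makes prophylaxis mandatory. The table's title fits the situation, and its antibody-only columns say to give none. For a patient positive for HBV-DNA or HBsAg, paragraph and table agree that prophylaxis is given, but the table's start time belongs to a patient not yet dosed. With about 9 sites, similar patients could be handled differently for no reason other than which lines were read.

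What is at stake is patient safety and consistent conduct. Section 6.2.10 itself reports sporadic HBV reactivation with everolimus and says that antivirals during anti-cancer therapy reduce reactivation and the associated morbidity and mortality.

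**Working it through.** No arithmetic applies, so the check sets the passages side by side by marker pattern. Table 6 has five result columns: four positive patterns and one all-negative. Its three recommendations are read as covering columns 1-2, 3-4 and 5. That reading is an assumption about the table layout, and Table 7's two groups match it.

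**Step 1: suppose the title of Table 6 governs (results found on everolimus).**

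| Pattern | Text rule | Table 6 | Result |
|---|---|---|---|
| HBV-DNA positive, or HBsAg positive (columns 1-2) | Prophylaxis for the rest of treatment and 4 weeks after; treatment may continue | Prophylaxis, begun 1-2 weeks before the first dose | Agree that it is given; the start time is already past |
| HBV-DNA and HBsAg negative, HBsAb or HBcAb positive (columns 3-4) | Prophylaxis as above | None; monitor HBV-DNA every 3-4 weeks | Opposite instructions |
| All negative (column 5) | Not applicable | No specific action | No conflict |

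HBsAb and HBcAb are serology in the protocol's own terms: Section 7.2 lists them among the serologic markers. Two of the four positive columns therefore conflict on whether prophylaxis is given, and the other two on when it starts.

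**Step 2: suppose the lead-in governs (baseline results).** The start time before the first dose then makes sense, and the text rule stands alone for discovery on study. But Sections 6.2.10 and 7.1 make patients with positive serology at screening ineligible, so the positive columns cover patients those sections exclude. The title would be wrong, and no table would say what to do by marker for a patient found positive on study.

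**Step 3: do the eligibility passages settle the scope?** They do not, because they differ among themselves. Criterion 9 turns on known active infection or a positive PCR. A site applying only that criterion could enrol an antibody-positive patient with negative HBV-DNA, whom Sections 6.2.10 and 7.1 would turn away. That is the group in columns 3-4.

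**Step 4: Table 7.** Its antibody-only row starts a first antiviral at reactivation, which implies none before. Its other row adds a second antiviral, which implies one already running. Both fit Table 6. Table 7 excludes vaccinated patients from HBsAb positivity; Table 6 has no such limit. A vaccinated patient with HBsAb alone falls in Table 6's monitoring column but not in Table 7's reactivation row.

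**The case against.** The strongest defence is that Table 6 concerns baseline results only, as its lead-in says, and that the paragraph separately covers discovery on study. On that reading the two do not collide and the timing is sensible. This has real force, and the lead-in must be weighed with the title. It does not clear the point: the title says otherwise, and the reading leaves the positive columns to patients whom Sections 6.2.10 and 7.1 exclude.

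A second defence is that the word appropriate in the text rule defers to Table 6, so that for antibody-only patients it can mean none. That sits badly with a mandatory instruction to receive prophylaxis for the rest of treatment, and it does not mend the start time.

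Three stronger readings are tempting and are not supported:

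- A reader might infer that the protocol is silent on whether everolimus continues in a patient found positive. It is not: the text rule says such patients may continue. The gap is that this permission is not reconciled with Table 6's lead time.
- A reader might infer that prophylaxis cannot be given at all to HBV-DNA- or HBsAg-positive patients found on treatment. The text rule gives a period that such a patient can follow; only Table 6's start time does not fit.
- A reader might take Table 7 as independent proof that Table 6 is right for patients found on study. Table 7 is keyed to baseline results, so it shows consistency with Table 6 and no more.

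It also stands that the situation should be uncommon. No on-treatment serology is scheduled, so discovery in a patient not tested at baseline would be incidental.

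**Conclusion.** The inconsistency is real and should be corrected. The scope of Table 6 is contradictory, and neither reading leaves Section 6.2.10 consistent: under the title, antibody-only patients get opposite instructions and the others a start time that has passed; under the lead-in, the positive columns apply to excluded patients and the title is wrong. The vaccination mismatch between Tables 6 and 7 is a smaller part of the same problem.

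The documents give no frequency for on-study discovery. Few patients are likely to be affected out of a planned enrolment of 46, given baseline-only testing in at-risk patients. The count of two conflicting columns out of four describes the table, not a share of patients. Nothing here changes the sample size, the primary endpoint or its analysis. The conclusion rests on reading Table 6's recommendations as spanning columns 1-2 and 3-4. It takes no view on which clinical rule is right.

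**What to change.** Reconcile these passages in one clarification: the Section 6.2.10 paragraph on patients found positive on study; the title, lead-in and columns of Table 6; Table 7, including how HBsAb after vaccination is treated in the two tables; and the eligibility statements in Section 3.2 (criterion 9), Section 6.2.10 and Section 7.1. The result should state whether Table 6 applies to baseline results, on-study results or both, and should give each serology pattern found on study one consistent instruction that can be carried out for a patient already on everolimus. The sponsor decides which clinical rule stands, including the timing and the handling of vaccinated patients.

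The cost is a protocol clarification of a few sentences and two tables, with the usual review. No change to data collection or to the SAP follows from the reconciliation itself.
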